**Figure 2. Management of Moderate (Grade 2) Infusion Reactions**

**Figure 3. Management of Severe (Grade 3 or Higher) Infusion Reactions**

**Table 8. Grading and Management of Allergic or Infusion-Related Reactions**

Adverse Event	Grade				
	1	2	3	4	5
Infusion-related reaction	Mild transient reaction; infusion interruption not indicated; intervention not indicated	Therapy or infusion interruption indicated but responds promptly to symptomatic treatment (eg, antihistamines, non-steroidal anti-inflammatory drugs [NSAIDS], narcotics, IV fluids); prophylactic medications indicated for ≤24 hours	Prolonged (eg, not rapidly responsive to symptomatic medication and/or brief interruption of infusion); recurrence of symptoms following initial improvement, hospitalization indicated for clinical sequelae	Life-threatening consequences; urgent intervention required	Death
Allergic reaction	Transient flushing or rash, drug fever <38.0°C. Intervention not indicated	Therapy or infusion interruption indicated but responds promptly to symptomatic treatment (eg, antihistamines, NSAIDS, narcotics, IV fluids); prophylactic medications indicated for ≤24 hours	Prolonged (eg, not rapidly responsive to symptomatic medication and/or brief interruption of infusion); recurrence of symptoms following initial improvement, hospitalization indicated for clinical sequelae (eg, renal impairment, pulmonary infiltrates)	Life-threatening consequences; urgent intervention required	Death
Anaphylaxis	–	–	Symptomatic bronchospasm, with or without urticarial; parenteral intervention indicated; allergy-related edema/angioedema; hypotension	Life-threatening consequences; urgent intervention required	Death
Cytokine release syndrome	Mild reaction; infusion interruption not indicated; intervention not indicated	Therapy or infusion interruption indicated but responds promptly to symptomatic treatment (eg, antihistamines, NSAIDS, narcotics, IV fluids); prophylactic medications indicated for ≤24 hours	Prolonged (eg, not rapidly responsive to symptomatic medication and/or brief interruption of infusion); recurrence of symptoms following initial improvement, hospitalization indicated for clinical sequelae (eg, renal impairment, pulmonary infiltrates)	Life-threatening consequences; pressor or ventilator support indicated	Death

Abstracted from NCI CTCAE Version 4.03.

### 10.3.3 Potential Immune Effects

An antibody blocking FcRn is anticipated to have several effects. These include acceleration of catabolism of IgG, but not other immunoglobulin isotypes such as IgA and IgM, leading to dose-dependent decreases in circulating IgG levels by up to an estimated 50% from the baseline levels

after a single dose and further decreases after multiple doses up to a 70% to 80% reduction. Based on studies in humans, it is expected that with a single dose, the nadir of this effect will occur approximately 5 days after dosing. The time course of recovery of IgG following dosing in the Phase 1a study suggests that a return to within 30% of baseline levels observed at pretreatment occurs within 4 weeks after a single dose and within 4 weeks after multiple doses as shown in NHPs.

Given the normal adult range of total IgG of 500 to 1600 mg/dL ([Agarwal and Cunningham-Rundles, 2007](#); [Furst, 2009](#); [Gonzalez-Quintela et al., 2008](#); [Jolliff et al., 1982](#); [Keystone et al., 2007](#); [McMillan et al., 1997](#); [van Vollenhoven et al., 2013](#)), with a mean of 1150 mg/dL, a 50% decrease in mean total IgG would translate to 575 mg/dL and a 50% decrease from the low end of the normal range used for the inclusion criteria of 600 mg/dL in this study would be to 300 mg/dL. An 80% decrease from baseline after multiple doses would result in IgG levels of 230 mg/dL and 120 mg/dL, respectively. While these levels are in the range found in patients with primary humoral immunodeficiency ([Ameratunga et al., 2013](#)), the levels will be transient. Further, as reported for other therapies used for pemphigus, the temporary (ie, less than 4 months) depletion of IgG (up to 95% reduction of total IgG as seen with immunoadsorption) does not appear to impart an increased risk of infection ([Eming and Hertl, 2006](#); [Furst, 2009](#); [Keystone et al., 2007](#); [Schmaldienst et al., 2001](#); [van Vollenhoven et al., 2013](#)). Study subjects will be monitored clinically for any infection. Further, commercial IVIG can be given to immediately restore IgG levels in case of a bacterial infection occurring while their IgG levels are decreased.

An antibody that blocks FcRn is expected to also down-modulate innate and adaptive immunity and the catabolism of IgG-containing ICs. Specifically, it is expected that anti-FcRn will promote the clearance of IgG-containing ICs and the effects of these ICs on stimulating innate immune cell production of inflammatory cytokines (eg, interleukin 12 [IL-12], interferon- $\gamma$ , and tumor necrosis factor) and inhibit the processing and presentation of antigens contained within ICs and thus the antigen-specific activation of CD4+ and CD8+ T-cells. Therefore, subjects with pre-existing conditions that are dependent upon IgG antibodies, such as chronic infections (eg, HIV, hepatitis B virus [HBV] or hepatitis C virus [HCV]), will be excluded from this study, as will subjects with active infection, in general.

#### **10.4 Events of Special Interest**

Not applicable.

#### **10.5 Other Safety Considerations**

##### **10.5.1 Laboratory Data**

All laboratory data obtained during the study should be reviewed. Any abnormal value that leads to a change in subject management (eg, requirement for additional medication or monitoring) or is determined to be of clinical significance by the Investigator should be reported as an AE and/or SAE as appropriate, unless this value is consistent with values obtained before entry into the study.

### 10.5.2 Medication Errors

Any medication error that results in an AE, even if it does not meet the definition of serious, requires reporting within 24 hours to the safety Medical Monitor. Refer to [Section 10.2.3.2](#) for more information.

### 10.5.3 Overdose

For the purposes of this study, an overdose of SYNT001 is defined as a dose that is two-fold higher than the intended dose for the subject. As all dosing for this study will be conducted in a controlled clinical setting, an overdose is not anticipated. In the unlikely event an overdose should occur, it should be reported as an AE.

### 10.5.4 Pregnancy

If a female subject or the female partner of a male subject becomes pregnant during the course of the study, the Investigator must report the pregnancy to Medpace Safety using the **Pregnancy Reporting Form** within **24 hours** of becoming aware of the event. The Investigator must obtain consent to collect pregnancy information (including the status of the newborn, if applicable).

If some of the information required for completion of the Pregnancy Reporting Form is unavailable at the time of the initial report, follow-up reports will be completed and submitted within 24 hours of becoming aware of the new information. Any pregnancy will be followed through delivery for the observation of any SAEs. Any SAE that occurs during pregnancy must be recorded on the SAE report form in the EDC system (eg, maternal serious complications, therapeutic or spontaneous abortion, ectopic pregnancy, stillbirth, neonatal death, congenital abnormality, birth defect) and reported within 24 hours in accordance with the procedure for reporting SAEs (see Section 10.2.3.2).

## **11. STATISTICAL CONSIDERATIONS**

### **11.1 General Design**

This study is being conducted to evaluate the safety, tolerability, PK, PD, activity, and immunogenicity of SYNT001 in pemphigus patients.

### **11.2 Study Populations**

Three populations will be employed in the analysis of study data:

- The **Safety** population will consist of all subjects who have received at least one dose of study drug.
- The **PD** population will consist of all subjects who receive at least one dose of study drug and have post-dose PD data available.
- The **PK** population will consist of all subjects who receive at least one dose of study drug and have post-dose PK data available.

Primary safety analyses will be performed on the Safety population. Demographics, subject disposition, screening, and baseline characteristics will be summarized for the Safety, PK, and PD populations, where appropriate.

### **11.3 Sample Size Justification**

Formal sample size calculations were not performed. The number of subjects was chosen based on feasibility and was considered sufficient to meet the study objectives.

### **11.4 Statistical Analysis**

#### **11.4.1 Statistical Analysis Plan**

Detailed methodology for summary and statistical analyses of the data collected in this study will be documented in a statistical analysis plan (SAP). The SAP may modify the plans outlined in the protocol; however, any deviations from the previously approved statistical plan will be described and justified in a SAP amendment. Additional statistical analyses other than those described in this section may be performed if deemed appropriate and will be described in the SAP. The SAP will be finalized prior to database lock.

Statistical analyses will be performed using Statistical Analysis System (SAS) software version 9.4 or later (Cary, NC). All clinical data captured will be provided in data listings.

Methods of handling of missing data for different endpoints will be further specified in the SAP. In general, where individual data points are missing because of insufficient samples, dropouts, or other reasons, the data will be analyzed based on reduced denominators unless specified otherwise in the SAP.

## 11.4.2 Statistical Methodology

All clinical data captured will be provided in data listings. Subject disposition, demographic information, and baseline characteristics will be presented. Baseline will be defined at the last value obtained prior to the first dose of study drug. Results will be summarized by dose level and cohort. Any discrepancy between treatment to be given and treatment received will be accounted for in these displays.

Continuous data will be summarized using descriptive statistics: number of subjects (N), number of observations (n), mean, median, standard deviation (SD), minimum, and maximum.

Categorical data will be summarized using frequencies and percentages. When categorical data will be presented, the percent will be suppressed when the count is zero to draw attention to the non-zero counts. The denominator for all percentages, unless otherwise specified, will be the number of subjects in the specified analysis population.

## 11.4.3 Analysis of Primary Endpoints

### 11.4.3.1 Safety Analysis

All statistical analysis of safety outcomes will be descriptive. The evaluation of SYNT001 based on vital signs, physical examination, ECGs, clinical safety laboratory tests, the incidence of AEs, TEAEs, and SAEs will be summarized by dose and dose regimen, severity, and relationship to study drug.

TEAEs will be summarized using the Medical Dictionary for Regulatory Activities (MedDRA®; Version 19 or higher) System Organ Class (SOC) and preferred term, classified from verbatim terms. The incidence and percentage of subjects with at least one occurrence of a preferred term will be included, using the most severe grade. The number of events per preferred term will also be summarized. Causality (relationship to study drug [related/not related]) will be summarized separately.

TEAEs, SAEs, and AEs leading to withdrawal, dose modification, or treatment discontinuation will be listed by subject per SOC and preferred terms. Duration of AEs will be determined and included in listings, along with action taken and outcome.

Laboratory results will be summarized by visit, time point, dose, and dose regimen. The incidence of laboratory abnormalities will be summarized. The worst on-study grade after the first dose of study drug will be summarized. Results for variables that are not coded will be presented in the listings as below, within, and above the normal limits of the central laboratory.

Vital sign measurements and change from baseline will be summarized at each scheduled time point by cohort using descriptive statistics.

Arithmetic mean of parameters from triplicate ECG will be calculated first for each subject at each planned time point. Then summary statistics of ECG test parameters (mean of triplicate) and change from baseline to each post-dose time point will be calculated. Shift tables for ECG test result category change (normal, abnormal, clinically abnormal) from pre-dose to each post-

dose time point showing number and percentage of subjects with movement between categories will be presented by treatment group. Frequency and percentage of subjects experiencing potential QTc prolongation ( $QTcF > 450$ ) will be summarized at each time point by cohort.

Concomitant medications will be coded using WHO Drug Dictionary (WHO-DD March 2013, Type B2 or later) and the data will be summarized and presented in tables and listings.

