	
Baseline characteristics to include medical history, physical examination, vital signs, and ECG will be summarized using descriptive statistics by dose, dose regimen, and visit.
 
Safety analysis
 
The evaluation of SYNT001 based on vital signs, physical examination, ECGs, clinical safety laboratory tests, the incidence of AEs, TEAEs, and SAEs summarized by dose and dose regimen, severity, and relationship to study drug.
 
Dose-finding analysis
 
The evaluation of SYNT001 based on total IgG levels and responses on the PDAI total activity score from baseline will be summarized using descriptive statistics by dose and dose regimen, visit and time point, as applicable.
 
Statistical methodology
 
Treatment-emergent AEs (TEAEs) will be summarized using the Medical Dictionary for Regulatory Activities (MedDRA®; Version 19 or higher) System Organ Class (SOC) and preferred term, classified from verbatim terms. The incidence and percentage of subjects with at least one occurrence of a preferred term will be included, using the most severe grade. The number of events per preferred term will also be summarized. Causality (relationship to study drug [related/not related]) will be summarized separately.
 
TEAEs, SAEs, and AEs leading to withdrawal, dose modification, or treatment discontinuation will be listed by subject and dose using SOC and preferred terms. Duration of AEs will be determined and included in listings, along with action taken and outcome.
 
Laboratory results will be summarized by time point, dose, and dose regimen. The incidence of laboratory abnormalities will be summarized. The worst on-study grade after the first dose of study drug will be summarized. Results for variables that are not coded will be presented in the listings as below, within, or above the normal limits of the central laboratory. Vital sign measurements and change from baseline will be summarized at each scheduled time point using descriptive statistics. PD/PK results will be summarized by dose and dosing regimen. Descriptive statistics of PD/PK parameters for SYNT001 will include mean, standard deviation (SD), coefficient of variation (CV), median, minimum, and maximum.
 
Immunogenicity results will be summarized by cohort, visit and time point. Descriptive statistics will include mean, SD, CV, median, minimum, and maximum.
 
Disease activity marker results will be summarized by dose, dose regimen, and visit. Descriptive statistics will include mean, SD, median, minimum, and maximum.
 
PDAI results will be summarized by score (total activity score, total damage score), cohort, and visit. Descriptive statistics will include absolute change from baseline and percent change from baseline.
 
Additional statistical analyses may be performed.

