- b. **Vital sign** measurements (sitting blood pressure, heart rate, respiratory rate, and oral temperature) to be obtained after 5 minutes of seated rest. Any abnormal measurements are to be repeated after 5 minutes of rest. On Days 0, 7, 14, 21, and 28, vital sign measurements will be collected immediately prior to the infusion; 15, 30, and 45 minutes after the start of the infusion; at completion of the infusion; and 30 minutes, 1 hour, and 2 hours following completion of the infusion.
- c. **Pulse oximetry**: On Days 0, 7, 14, 21, and 28, pulse oximetry to be measured immediately prior to the infusion; 15, 30, and 45 minutes after the start of the infusion; at completion of the infusion; and 30 minutes, 1 hour and 2 hours following completion of the infusion.
- d. **Clinical safety labs**: hematology, clinical chemistry, and urinalysis (see [Section 7.5](#) for a complete list). Full clinical safety laboratory draws will be collected at screening and on Days 0, 7, 14, 21, 28, 33, 42, 56, 84, and 112.
- e. **Pregnancy test (women of childbearing potential only)**: To be performed at time of screening, prior to first dose of SYNT001 on Day 0, and on Days 56 and 112. Urine or serum test is acceptable; however, positive urine tests must be confirmed with serum testing.
- f. Digital 12-lead **ECG** to be obtained in triplicate at least 1 to 2 minutes apart and after 5 minutes of rest in a supine position. See [Section 7.6](#) for additional information. On Days 0 and 28 to be obtained 5 minutes after the completion of infusion. Day 12 ECG will be collected only if the visit is conducted at the study site.
- g. **Serology**: Testing at Day 56 will not be done for any subject whose baseline titer is below the level of detection. If the Day 56 results are greater than 30% below the baseline value, or if the subject falls below the level of detection, the subject will be re-tested at Day 84; if still below the baseline value (or level of detection), the subject will be re-tested at Day 112. Any subject whose baseline value for tetanus or VZV was above the detectable level at baseline, and is not within 30% of the baseline value or is below the detectable level by Day 112, will be referred to their primary care physician for further management. See [Section 7.5.3](#) for additional information.

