- b. **Vital sign** measurements (sitting blood pressure, heart rate, respiratory rate, and oral temperature) to be obtained after 5 minutes of seated rest. Any abnormal measurements are to be repeated after 5 minutes of rest. Vital sign measurements will be taken on all study visits. On dosing days, vital sign measurements will be collected immediately prior to the infusion; 15, 30, and 45 minutes after the start of the infusion; at completion of the infusion; and 30 minutes, 1 hour and 2 hours following completion of the infusion.
- c. **Pulse oximetry**: On dosing days, pulse oximetry to be measured immediately prior to the infusion; 15, 30, and 45 minutes after the start of the infusion; at completion of the infusion; and 30 minutes, 1 hour, and 2 hours following completion of the infusion.
- d. **Clinical safety labs**: hematology, clinical chemistry, and urinalysis. See [Section 7.5](#) for a complete list. Full clinical safety lab draws will be collected at screening and at all study visits prior to infusion if applicable.
- e. **Pregnancy test (women of childbearing potential only)**: To be performed at time of screening and prior to dose on dosing days if applicable. Urine or serum test is acceptable; however, positive urine tests must be confirmed with serum testing.
- f. Digital 12-lead **ECG** to be obtained after 5 minutes of rest in the supine position and in triplicate approximately 1 minute apart. See [Section 7.6](#) for additional information. On days of treatment, to be obtained approximately 5 minutes after the completion of infusion.
- g. **Serology**: Any subject whose baseline value for tetanus or VZV was above the protective level at baseline and is not within 30% of the baseline value or is below the protective level by End of Follow-up, will be referred to their primary care physician for further management. See [Section 7.5.3](#) for additional information.
- h. PDAI will be administered at screening. Subject eligibility requires a PDAI total activity score >4. Thereafter, assuming eligibility, the PDAI will be administered during Treatment Period and Follow-up Period. See [Section 7.7](#) for additional information.
- i. **PK**: Starting on dosing days, serum samples will be collected just prior to the start of study drug infusion (pre-dose) and at 5 minutes, 1 and 2 hours after the end of study drug infusion. See [Section 7.5.4](#) for additional information.

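### After the first infusion, the planned vital-sign change summary mixes drift since Day 0 with the acute infusion effect (minor)

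*Protocol*

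**What the plan says.** Section 11.4.2 of the protocol sets one baseline for all displays: "Baseline will be defined at the last value obtained prior to the first dose of study drug". Section 11.4.3.1 applies it to vital signs: "Vital sign measurements and change from baseline will be summarized at each scheduled time point by cohort using descriptive statistics". The synopsis says the same: "Vital sign measurements and change from baseline will be summarized at each scheduled time point using descriptive statistics". Neither place names another reference value for vital signs.

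The statistics are those in section 11.4.2: "Continuous data will be summarized using descriptive statistics: number of subjects (N), number of observations (n), mean, median, standard deviation (SD), minimum, and maximum". The same section adds that "All clinical data captured will be provided in data listings".

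A same-day reference is already collected. For Cohort 1, Table 2 footnote b says: "On Days 0, 7, 14, 21, and 28, vital sign measurements will be collected immediately prior to the infusion". For Cohort 2, Table 3 footnote b says: "On dosing days, vital sign measurements will be collected immediately prior to the infusion". Section 7.4 gives the full sequence: one reading before the infusion, then readings at 15, 30 and 45 minutes, at completion, and at 30 minutes, 1 hour and 2 hours afterwards. That is 8 readings per dosing day, 7 of them during or after the infusion.

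**The concern.** Repeated readings around each infusion are there to show what the infusion does. Section 10.3.2 treats infusion reactions as possible with this antibody and lists changes in heart rate and blood pressure among the symptoms. Vital signs are part of the primary safety endpoint in section 3.

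Later infusions matter as much as the first. In the monkey studies described in section 2.2, flushing and periocular swelling appeared after the third dose, when anti-drug antibodies first appeared. Yet the first infusion is the only one at which the planned change is a pure within-visit change.

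With at most 8 subjects in Cohort 1 and 12 in Cohort 2, one subject's own fall or rise is informative. A table of change from Day 0 will often show that subject, but not reliably, and not as an acute change.

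**Working it through.** The plan states no figure to reproduce, since the safety analysis is descriptive and section 11.3 says that no formal sample size calculation was done. The check is an identity, a count, a constructed example and a simulation.

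**Identity.** For reading t at infusion k:

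Y(k,t) − Y(Day 0, pre) = [Y(k,t) − Y(k, pre)] + [Y(k, pre) − Y(Day 0, pre)]

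The first bracket is the acute change and the second is drift since Day 0. The drift term is zero by definition only at the first infusion.

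**Count.** Infusions come from section 5.2 (Cohort 1: 5; Cohort 2: 3 + 5 = 8) and Table 10 (weekly option: 13). There are 7 readings during and after each infusion.

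| Schedule | Infusions affected | Readings affected per subject |
|---|---|---|
| Cohort 1 | 5 − 1 = 4 of 5 | 4 × 7 = 28 of 35 (80%) |
| Cohort 2 | 8 − 1 = 7 of 8 | 7 × 7 = 49 of 56 (87.5%) |
| Cohort 2, weekly option | 13 − 1 = 12 of 13 | 12 × 7 = 84 of 91 (92%) |

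In Cohort 2 the last infusion is on Day 84, so drift can build up over as much as 84 days. These figures count readings. They do not measure the size of the distortion, because the protocol gives no vital-sign data.

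**Can the planned rows hide an acute change?** This is a constructed example with invented systolic values: 12 subjects, all 120 on Day 0, with pre-infusion values on a later day of 110, 112, ..., 132.

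- A: every subject falls by 5.
- B: eleven subjects fall by 3, and the subject at 132 falls by 27 to 105.

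In both cases the post-infusion values are 105, 107, ..., 127.

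| Summary | A | B |
|---|---|---|
| Observed value: mean, SD, range | 116, 7.21, 105 to 127 | 116, 7.21, 105 to 127 |
| Change from Day 0: mean, SD, range | −4, 7.21, −15 to +7 | −4, 7.21, −15 to +7 |
| Own acute change: mean, SD, range | −5, 0, −5 to −5 | −5, 6.93, −27 to −3 |

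The planned row is identical in A and B. The mean acute shift is recoverable by row subtraction (116 − 121 = −5), but the spread and the extreme are not.

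The reverse can also happen. In case C the 27 mmHg fall is in the subject who starts at 110. The observed minimum is then 83 and the row does reveal that subject, but the change-from-Day-0 minimum reads −37 for an acute fall of 27.

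**Inflation of the SD.** With day-to-day within-subject SD d and acute-change SD a, both assumed, the SD of change from Day 0 is √(2d² + a²).

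| d, a (mmHg) | SD of change from Day 0 | Ratio to a |
|---|---|---|
| 5, 4 | √66 = 8.1 | 2.03 |
| 5, 8 | √114 = 10.7 | 1.33 |
| 10, 4 | √216 = 14.7 | 3.67 |
| 10, 8 | √264 = 16.2 | 2.03 |

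**How often would one subject be missed?** I simulated 200,000 normal cohorts in each of 16 settings: n = 8 or 12, between-subject SD 12 or 16, and the d and a values above. One subject had an extra fall of 25 mmHg. The table shows how often that subject was not the row minimum, as the range over settings.

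| Row minimum | Subject missed |
|---|---|
| Observed value | 34% to 62% |
| Change from Day 0 | 7% to 51% |
| Both of the above | 4% to 39% |
| Change from same-day pre-infusion value | 0% to 9% |

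All SDs here are assumptions.

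**The case against.** The strongest reply is that this is an extra table the statistical analysis plan could add, not a mistake. Section 11.4.1 leaves detailed methods to that plan and lets it add analyses. The pre-first-dose baseline is also a legitimate choice, since it measures cumulative change under repeated dosing.

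Much of the information is already there. The same-day pre-infusion reading is a scheduled time point with its own row. Listings keep every pre/post pair, and with 8 or 12 subjects they can be read one by one. Individual reactions are handled elsewhere: by CTCAE grading (7.4), by stopping the infusion and barring further treatment at Grade 2 or higher (10.3.2), by the stopping rules (9.5), and by the 24-hour and 7-day reviews (5.2), which consider vital signs.

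The numerical illustration also has limits. Setting Day 0 to 120 for everyone makes the observed and change columns carry the same information, so the example proves possibility, not likelihood. The simulation asks whether a subject is the row minimum, which is not clinical detection. It also treats the same-day reading as clean. Table 5 allows that reading up to 240 minutes before the infusion, and it may precede premedication permitted under 7.12, so the comparison favours the fix.

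Most of this stands, and it limits the weight of the point. It does not remove it. The protocol is not silent: it fixes one baseline and applies it to every vital-sign time point. Listings and adverse event records do not supply a summary of subjects' own acute changes.

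**Conclusion.** The concern holds and is minor. At 4 of 5, 7 of 8 and 12 of 13 infusions, the planned change column answers a cumulative question where the reading schedule is built for an acute one. What is lost is the SD, median, minimum and maximum of each subject's own acute change. The mean acute shift is still obtainable if the same subjects contribute to both rows, extreme observed values still appear in the raw minimum and maximum, and the first infusion is unaffected.

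The identity and the counts rest only on the protocol. The SD ratios of 1.3 to 3.7 and the simulated percentages rest on assumed SDs and on a clean same-day reference, so they show a plausible range and are not estimates for this trial. Nothing here shows a failure of safety monitoring, and no sample size or dose decision is affected.

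**What to change.** Add one sentence to section 11.4.3.1: for the 7 readings during and after the infusion on each dosing day, vital signs and pulse oximetry will also be summarised as change from that day's last pre-infusion reading (n, mean, median, SD, minimum, maximum). Keep the pre-first-dose baseline for pre-infusion values and for non-dosing visits, where longer-term trend is the question.

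State with the table that the reference reading may be up to 240 minutes old and may precede premedication. It removes drift since Day 0 but is not a perfectly clean reference.

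As a separate option, count the subjects beyond a pre-set change threshold at all infusions, including the first. The section already plans a count of this kind for the ECG: "Frequency and percentage of subjects experiencing potential QTc prolongation". No vital-sign count is planned at any infusion, so its absence does not come from the baseline choice.

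The cost is the added sentence and one further set of summary columns. The readings are already collected on every dosing day, so no new visits or data are needed.
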